### **Distress Protocol for high risk of depression or anxiety**

### **HADS** score

• A participant scores 12 or above on the Hospital Anxiety and Depression Scale. This is the threshold identified for patients with ESKD that indicates that there is a risk that the person is experiencing clinical depression or anxiety.

### Response

- •Researcher will explain to the participant that the scale is not diagnostic but that their score indicates that they may benefit from a mental health assessment. Permission will be sought to speak to the nurse in charge about onward referral, this could include their GP for general mental health services or the renal counselling services for specialised health psychology services.
- •If there is an identified risk of suicide the Distress Protocol for suicide risk will be put into effect.
- If there is no identified risk to the participant or anyone else confidentiality will not be breached without their permission. Participant will be provided with information on supportive services

- •Follow up participant during next visit to the unit, with the patient's consent.
- •If participant has declined referral this decision will be reviewed during the follow up data collection.
- •As participants are not being excluded as a consequence of mental health issues, they will be asked if they wish to continue in the study. If the participant wishes to continue in the study risk will be reviewed at each follow-up session.

Methodology in arts-based intervention research needs to be considered due to the lack of randomised controlled trials (Bungay et al., 2014; Boyce et al., 2017). Arts-based interventions meet the Medical Research Council's description of a complex intervention (Medical Research Council, 2009), in that it involves several interacting components that can impact on implementation, evaluation and the context in which it is delivered. There is a tendency of complex interventions to fail to show a significant effect in randomised controlled trials (Levati et al., 2016). This absence of detectable effect may not result from an ineffective intervention, but instead could be a consequence of the logistical difficulties in standardising and evaluating complex health interventions in an experimental process (Medical Research Council, 2009). Consideration needs to be given to optimising the intervention and the trial process, such as recruitment procedures and randomisation, for the context in which the intervention will be delivered. To address these issues Levati et al. (2016) recommend feasibility studies. These focus on real world implementation during the development of the intervention and research design, by involving key stakeholders throughout each stage of the process and 'in vivo' exploration of problems that occur with implementation and trial processes during feasibility testing.

When exploring staff perceptions of arts-based interventions, the focus in the literature is on how the intervention impacts the patients, with fewer studies examining the effect of the intervention on healthcare staff themselves (Bungay *et al.*, 2014; Boyce *et al.*, 2017). Due to the unique nature of the clinical working environment it is particularly important to consider the acceptability of an intervention for healthcare staff (May, 2013). The acceptability for patients must also be taken into consideration. If an effective intervention is burdensome or

non-engaging, patients will not participate and therefore not experience potential benefits (May, 2013). In order to evaluate whether an intervention is acceptable in practice, a process evaluation must be conducted. Process evaluations provide a detailed understanding of complex interventions by examining their implementation, mechanism of impact and context (Moore *et al.*, 2015).

The All Party Parliamentary Group report on the Arts for Health and Wellbeing (All-Party Parliamentary Group on Arts Health and Wellbeing, 2017) reflects the lack of costeffectiveness analysis and economic evaluations conducted for arts-based interventions (Craemer, 2009). Cost-effectiveness analyses are important as they are the basis of decision making for health intervention recommendations by National Institute for Health and Care Excellence (NICE) (Ogden, 2017). In order to ensure that the effectiveness of an intervention can guide healthcare policy, economic evaluations and cost-effectiveness analysis are needed to establish justification for funding. However, due to the absence of economic evaluations for arts-based interventions implemented within hospital settings, it is important to explore the best methods for conducting such cost-effectiveness analyses.

The study will consist of four phases and will utilise a mixed-method design. Phase 1 will consist of the development of the intervention, phase 2 will involve a quantitative feasibility randomised controlled trial (RCT), phase 3 will involve a qualitative process evaluation and phase 4 will involve feasibility testing for an economic evaluation.

The RE-AIM mixed methods framework (Forman et al., 2017) will be used to guide the research process. The framework outlines the core aspects of a complex intervention that should be explored to enhance the generalisability of findings (Glasgow and Estabrooks, 2018). The core aspects include the intervention's reach, effectiveness, adoption, implementation and maintenance. Not all RE-AIM objectives can be met within a feasibility study, for example, the maintenance of the intervention over time. However the framework will be used to inform research questions, data collection and outcomes appropriate for a feasibility study.

1.1 Inclusion/Exclusion criteria

1.1.1 Inclusion criteria patients

- Age 18 or over
- Able and willing to participate

• Receiving haemodialysis

1.1.2 Exclusion criteria patients

- Unable to provide consent or participate due to lack of capacity or physical ability
- Under the age of 18
- Non-English speaking patients who are unable to understanding verbal or written communication without the aid of an interpreter.

1.1.3 Inclusion criteria healthcare staff

- A member of the multidisciplinary team, including nurses, healthcare support workers, doctors, dietitians, social workers and counsellors.
- Have had experience with the intervention.
- Have worked in a clinical renal setting for more than 3 months

1.1.4 Exclusion criteria healthcare staff

- Not a member of the multi-disciplinary team
- Have not experienced the intervention, either directly or in passing.
- Have not worked in the clinical renal setting for more than 3 months

Justifications for these inclusion and exclusion criteria are contained within the protocol.

2 Outcome measures

2.1 Primary outcome measures

- Phase 2 (Feasibility RCT): Feasibility of recruiting and retaining participants for a randomised controlled trial as determined by proportion of target sample size recruited and retained over 3 month follow up.
- Phase 3 (Process Evaluation): Acceptability of the intervention for patients and healthcare staff as reported during semi-structured interviews and focus groups.
- Phase 4 (Feasibility economic evaluation): Feasibility of using the Patient Resource Use Log to capture healthcare use data as determined by proportion of participants who complete the Patient Resource Use Log and proportion of missing data.

2.2 Secondary outcome measures

• Phase 2: Exploration of demographic factors that may influence recruitment and retention.

- Phase 2: Time taken for recruitment, data collection and data analysis.
- Phase 2: Acceptability of clinical outcome measures (Hospital Anxiety and Depression Scale (HADS), Kidney Disease Quality of Life – Short Form 36 (KDQOL-SF36)) as determined by completion rates and proportion of missing data.
- Phase 3: Perceptions of clinical outcome measures (Hospital Anxiety and Depression Scale, Kidney Disease Quality of Life – Short Form 36) from qualitative interviews and focus groups
- Phase 3: Experiences of implementation of the arts-based intervention from qualitative interviews and focus groups.
- Phase 4: Feasibility of using the EQ-5D-5L to calculate cost-utility values as determined by proportion of participants who complete the EQ-5D-5L and proportion of missing data.
- Phase 4: Cost of the intervention in terms of material price.

3 Data

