# Objectives:

- Develop an arts-based intervention for patients receiving haemodialysis, informed by a systematic literature review and an interdisciplinary advisory group.
- Identify best practice for implementing an arts-based intervention in a haemodialysis unit.
- Establish recruitment, retention and participation rates for a randomised controlled trial.
- Identify time needed for recruitment, data collection and data analysis.
- Explore the acceptability of an arts-based intervention for patients and staff on a haemodialysis unit.
- Explore the suitability of outcome measures.
- Identify estimated costs of delivering the arts-based intervention and methods for assessing cost-effectiveness in a full trial.
- Develop the protocol for a definitive randomised controlled trial and economic evaluation of an arts-based intervention compared to usual care.

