# **Phase 4 – Economic evaluation**

# Data collection and management

Feasibility studies do not have the sample size required for the statistical power needed to establish effectiveness, therefore conducting a full cost-effectiveness evaluation within a feasibility study is not recommended (Hounsome and Shearer, 2015). However the feasibility of data collection methods and the appropriateness of outcome measures can be evaluated during a feasibility study to inform a full economic evaluation within a definitive randomised controlled trial.

Health and social care costs of participants will be collected using Patient Service Use Logs previously used in the Palliative Care in Chronic Kidney Disease study (PACKS) (Agus *et al.* (2017). These logs will collect information on health and social care service use during the intervention. The logs will be collected post-intervention and at six weeks and three months follow up. The outcome of interest will be the feasibility of using a Patient Service Use Log in a full economic evaluation according to proportion of participants who complete the Patient Service Use Log.

The EQ-5D-5L will be administered to patients in conjunction with the clinical outcome measures, pre/post-intervention and at 6 weeks and 3 months follow up. The EQ-5D-5L is recommended by NICE for deriving utility values for the calculation of quality adjusted life years in cost-effectiveness analysis within definitive economic evaluations (National Institute for Health and Care Excellence, 2012) and has been shown to be a valid measurement of health status in patients with ESKD (Cleemput *et al.*, 2004). However it is important to consider the burden of questionnaires on participants during a randomised controlled trial. The acceptability of administering the EQ-5D-5L to patients in conjunction with the KDQoL-SF 36 and the HADS will be explored by examining the completion rates and proportion of missing data for the EQ-5D-5L.

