# Data analysis

A cost-consequence analysis is recommended by the National Institute of Health Research for both complex interventions and feasibility studies where the outcomes of interest are not clear (Hunter and Shearer, 2014). Costs and outcome measure data for both the intervention and control group will be presented using means and 95% confidence intervals in order to show a general overview of the economic costs of the intervention, and differences in resource use and outcome measures between groups. Completion rates and missing data for the Patient Service Use Log and the EQ-5D-5L will be presented as frequencies to assess the feasibility of data collection.

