6.4 Patient Resource Use Log (Administered at baseline, week 3, 6 and 12)

- Home care worker (nhs), no.(%) and mean (95%CI)
- Home care worker (paid), no.(%) and mean (95%CI)
- Meals on wheels (nhs), no.(%) and mean (95%CI)
- Meals on wheels (paid), no.(%) and mean (95%CI)
- Other care visits, no.(%) and mean (95%CI)
- GP visits at surgery, no.(%) and mean (95%CI)

- -Duration of visit, mean (95%CI)
- GP telephone consultations, no.(%) and mean (95%CI)
- GP Home visit, no.(%) and mean (95%CI)
- Calls to out-of-hours, no.(%) and mean (95%CI)
- Visits to out-of-hours, no.(%) and mean (95%CI)
- Nurse visits at surgery, no.(%) and mean (95%CI)
- Nurse telephone consultation, no.(%) and mean (95%CI)
- Community/district nurse home visit, no.(%) and mean (95%CI)
- Social worker visits, no.(%) and mean (95%CI)
- Occupational therapist visits, no.(%) and mean (95%CI)
- Other visits, no.(%) and mean (95%CI)
- Visits to A&E, no.(%) and mean (95%CI)
- Visits to hospital clinic (kidney related), no.(%) and mean (95%CI)
- -Duration of visit, mean (95%CI)
- Visits to hospital clinic (not kidney related), no.(%) and mean (95%CI)
- -Duration of visit, mean (95%CI), mean (95%CI)
- Admissions to hospital/ residential unit, no.(%) and mean (95%CI)
- -Duration of stay (days), mean (95%CI)

7 Additional information

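### The SAP's only outcome on intervention cost is material price, which is narrower than the protocol's objective of estimating delivery cost, and nothing visible records delivery time

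*SAP*

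**What the plan says.** Among the protocol's Objectives is to "Identify estimated costs of delivering the arts-based intervention and methods for assessing cost-effectiveness in a full trial". The one after it is to "Develop the protocol for a definitive randomised controlled trial and economic evaluation of an arts-based intervention compared to usual care". The protocol's Phase 4 data analysis section says that costs and outcomes will be presented for both groups "in order to show a general overview of the economic costs of the intervention", among other purposes.

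SAP 2.2 lists one Phase 4 item on what the intervention itself costs: "Cost of the intervention in terms of material price". The Phase 4 primary outcome in SAP 2.1 concerns a different kind of cost: "Feasibility of using the Patient Resource Use Log to capture healthcare use data". The protocol describes that instrument in the same way: "Health and social care costs of participants will be collected using Patient Service Use Logs". The single outcome on time in the SAP is "Time taken for recruitment, data collection and data analysis".

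**The concern.** The objective concerns the cost of delivery, while the outcome that should answer it covers only what is bought. Neither document explains the narrowing or says that the objective will be answered only in part.

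The omitted part may matter for this type of intervention. The protocol's Background says that the more dynamic arts-based interventions need facilitation, and contrasts them with music listening. The Randomisation section promises control participants a facilitated session after data collection and names it separately from the supplies they will receive. If the developed intervention is facilitated, the deliverer's time is part of its delivery cost.

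The protocol justifies the economic phase by the absence of economic evaluations of arts-based interventions in hospitals, and uses it to test whether cost data can be collected. If delivery time is not recorded, the study does not learn whether it can be recorded, and that bears on planning the later evaluation.

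**Working it through.** The plan states no cost figure, so there is none to reproduce. The check compares definitions and counts what is recorded.

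**Step 1. Compare the definitions.**
- Protocol, Objectives: the estimated costs of delivering the intervention, with no limit to materials.
- Protocol, Phase 4 data analysis: an overview of the intervention's economic costs, again with no such limit.
- SAP 2.2: material price.

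The SAP definition is a subset of the objective.

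**Step 2. Look for another outcome that covers the rest.** SAP 2.1 lists 3 outcomes and SAP 2.2 lists 7, so 3 + 7 = 10.
- On the cost of the intervention: 1 of 10 (material price).
- On time of any kind: 1 of 10, and it covers research processes. SAP 5 adds only that the time spent on the clinical-outcome analysis will be reported.
- On delivery or facilitator time: 0 of 10.

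**Step 3. Look for an instrument that would capture it.**
- SAP Table 1 has 10 patient rows and 3 healthcare-professional rows, so 10 + 3 = 13. None is a session or delivery record.
- SAP 6.4 lists 20 service lines and 4 duration lines, so 20 + 4 = 24. All concern patients' care contacts or admissions. The two catch-all lines for other visits sit within the same patient log. Delivery lines: 0 of 24.

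The log was never meant to cost the intervention, so its silence is not a fault in the log. The count shows only that the log does not fill the gap.

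**Step 4. Check the remaining places.**
- The Phase 1 literature review asks about implementation costs, but in published work. It records nothing in this trial.
- The Phase 3 outcomes on implementation are qualitative, and field notes appear only as a source for triangulation.
- The cost-consequence text (Protocol Phase 4, SAP 5) names no cost inputs and no source for delivery time.

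**Step 5. Size.** Delivery time cost = sessions × time per session × unit cost. The visible text gives none of the three, so no monetary figure or range is offered.

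**The case against.** The difference in wording is hard to dispute. The stronger objections concern what follows from it.

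- *The cost-consequence analysis may be broader.* A reader might infer that the intervention arm's cost will be understated there. The documents do not support that. Neither the protocol's Phase 4 text nor SAP 5 limits the inputs to materials; they do not list the inputs at all. The materials-only conclusion therefore holds for the SAP 2.2 outcome and not for everything Phase 4 may report. This objection stands.
- *The definitive trial need not rest on this figure.* A reader might also infer that its economic evaluation would start from the materials cost. Nothing in the documents says so, and the same objective also covers methods for assessing cost-effectiveness. This stands.
- *Facilitation is not established.* The Background describes a class of interventions, the session promised to controls comes after data collection, and the visible text does not say who delivers the sessions. This stands: facilitation is likely, not certain.
- *The objective asks only for estimated costs.* An estimate could be built afterwards from session schedules, participation rates and the structured description of the intervention that Phase 1 plans. That is possible, but neither document plans it, and schedules would not necessarily show preparation time. This stands in part.
- *Removed appendices might hold a delivery record.* This cannot be excluded. However, SAP 6.4 sets out the log items to be analysed, and none concerns delivery.
- *The outcome is minor.* It is one of seven secondary outcomes, the study does not attempt a full cost-effectiveness analysis, and the progression criteria turn on recruitment and acceptability. This stands and sets the severity.

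**Conclusion.** The point holds in a limited form. The SAP's definition of intervention cost is narrower than the protocol objective it serves, and nothing in the visible text records delivery time. Followed as written, the SAP 2.2 outcome meets that objective for materials only.

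The coverage gap can be counted, but its monetary size is unknown. The mismatch in definition rests on the text alone. Its practical importance rests on the assumption that the developed intervention will need someone's time to deliver, which the protocol makes likely but does not settle. No claim is made that the comparison of costs between arms would be biased. Progression is unaffected. This is a cheap improvement of low severity.

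**What to change.** 1. In SAP 2.2, redefine the Phase 4 cost outcome as delivery cost: materials plus the time of whoever delivers the sessions, with the two parts reported separately.
2. Take the time from a brief record completed for each session. Keep it as a delivery record rather than as a patient assessment in Table 1.
3. Name in the SAP the source of the unit cost used to value that time, for example the rate actually paid.
4. In SAP 5, name both components as intervention-arm inputs to the cost-consequence analysis.

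If this is not wanted, one sentence in SAP 2.2 saying that the delivery-cost objective is met for materials only would make the plan consistent.

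The full change costs one reworded outcome, one added sentence in SAP 5, a short form and a named unit-cost source. The downside is a little extra recording by whoever delivers the sessions and a higher reported intervention cost. The record is best in place before sessions begin. If unit staff also spend time supporting sessions, the SAP should say whether that time counts, because materials plus deliverer time would not capture it.

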3.1 Management of data sets

Data will be collected and analysed by the PhD student responsible for this study, with oversight and supervision from the PhD supervisory team and guidance from a University Statistician. Quantitative data will be analysed using Statistical Package for the Social Sciences (SPSS v 24), while qualitative data for the process evaluation will be digitally recorded and transcribed verbatim prior to data analysis. All data will be stored in accordance with the Data Protection Act (2018) participants will be provided an anonymous code and identifiable information will be removed from the qualitative data to maintain confidentiality. A more detailed overview of data storage and management is included in the study protocol, and an overview of the timing of data collection can be seen in Table 1.

| Table 1 | Screening Baseline | Post intervention/ 3 weeks | 6 weeks | 3 months (12 weeks) |
|---|---------------------------|----------------------------------|---------|------------------------|
| PATIENT | | | | |
| Informed Consent | Х | | | |
| Inclusion/Exclusion Criteria | X | | | |
| Demographic Data | Х | | | |
| 9-point Clinical Frailty Scale | x | | | |
| KDQOL-SF36 | x | x | X | X |
| EQ-5D-5L | X | X | X | X |
| HADS | x | x | X | x |
| Patient Service Use Log | x | X | X | x |
| Diabetes and diabetic comorbidity check | x | X | X | x |
| Qualitative interview | At one point during study | | | |
| HEALTHCARE PROFESSIONALS | | | | |
| Informed Consent | X | | | |
| Inclusion/Exclusion Criteria | x | | | |
| Qualitative interview | At one point during study | | | |

4 Sample Size Calculation

4.1 Sample size for feasibility RCT and economic evaluation

A sample size of 30 is recommended by the NIHR's Research Design Service for the estimation of a parameter, such as sample size, recruitment or attrition rate, for a definitive randomised controlled trial, although they recognise that advice varies from 24 to 50 participants. Due to the increased risk of identifying a statistically significant result with larger sample sizes, and practical limitations of a small, single centre study, a sample size of 30 was selected for the feasibility RCT. A university statistician was consulted who confirmed that a sample of 30 was an appropriate sample size to meet the objectives of the study. A more comprehensive overview of the sample size decision is available in the study protocol.

4.2 Sample size for Process Evaluation

Approximately 13 patients will be recruited into the process evaluation. Simulations have shown that this sample size of 10 should identify 80% of problems within a complex intervention (O'Cathain et al., 2014), while data saturation is likely to be reached at 12 interviews on average (Guest et al., 2006). The principle of 10 + 3 for data saturation outlines that a minimum of 10 interviews should be conducted, followed by at least 3 consecutive interviews that present no new findings (Francis et al., 2010), therefore a sample of 13 patients will be recruited for semi-structured interviews. Approximately 5 healthcare staff will be recruited into each focus group, with a proposed total of 3 focus groups (Schneider *et al.*, 2009). The dialysis unit in which the study is taking place is relatively small, therefore the focus groups will be limited by the amount of staff available who meet the eligibility criteria and the requirement to produce a manageable amount of data for the time limitations of the study (Carlsen and Glenton, 2011; O'Cathain et al., 2014). However, these are approximate sample sizes, and data collection will continue until data saturation is reached. The researcher will provide the participants with a consent form prior to commencement of the focus group (Appendix 6). Data saturation will be determined when there is no new data being found from which additional themes can be developed (Guest et al., 2006).

5 Analysis Principles

Baseline demographic and clinical data will be analysed using descriptive statistics. Categorical data will be presented as frequencies and percentages, while continuous data will be presented as means and standard deviations

Primary quantitative outcomes: Recruitment, participation and retention rates will be reported and presented in a CONSORT flow diagram (Eldridge *et al.*, 2016). Data on patients who were eligible for recruitment, who consented to participation, who completed the study, and completion of the Patient Resource Use Log will be presented as proportions and rates.

Secondary quantitative outcomes: Chi squared tests will be conducted to establish whether the experimental and control group differ significantly in baseline demographic and clinical data. Completion of the KDQOL-SF36, HADS and EQ-5D-5L will be presented as proportions and rates. A cost consequence analysis will be used to provide a comparative overview of differences in costs and outcomes of participants in the experimental and control group.

Qualitative outcomes: The semi-structured interviews and focus groups will be recorded and transcribed verbatim. Inductive thematic analysis will be used to analyse the data collected. Investigator triangulation, method triangulation and data source triangulation will be used to ensure validity of the identified themes. A more comprehensive description of qualitative analysis is available in the study protocol.

Clinical outcomes: Exploratory inferential statistics will be conducted, but no conclusions on the effectiveness of the intervention will be made from the results. Independent t-tests (or the non-parametric equivalent Mann-Whitney U) will be conducted to compare the scores of the experimental group and control group. The majority of arts-based intervention research involves pre-and-post-test designs; therefore a repeated measures t-test (or the non-parametric equivalent Wilcoxon Matched Pairs test) will also be conducted to compare the mean scores of the experimental before and after receiving the intervention. An analysis of variance will be conducted to explore any potential sub-group analysis that may be relevant within a future RCT. The amount of time taken to conduct this analysis will be reported to inform feasibility.

6 Analysis details

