6.2 Patient Baseline Characteristics

The median (interquartile range) will also be presented for skewed data

- Age, mean (SD)
- Gender, no.(%)
- Education, no.(%)
- Dialysis vintage, mean (SD)
- Ethnicity, no.(%)
- Clinical Frailty Scale, no.(%)
- Number of co-morbidities, mean (SD)
- KDQOL-SF36
- EQ-5D-5L
- HADS
- Patient Resource Use Log

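### The SAP's only baseline test (chi-squared) does not fit the continuous variables, and the arm comparison of clinical scores is undefined and unadjusted for baseline

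*SAP*

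**What the plan says.** **Baseline.** SAP section 5 first says that "Baseline demographic and clinical data will be analysed using descriptive statistics", then under secondary quantitative outcomes adds that "Chi squared tests will be conducted to establish whether the experimental and control group differ significantly in baseline demographic and clinical data". No other baseline test is named. The protocol (Phase 2, Feasibility measures) counts age, dialysis vintage, number of co-morbidities and frailty among the baseline demographic and clinical data. SAP section 6.2 summarises the first three by mean and SD, and notes that "The median (interquartile range) will also be presented for skewed data". The protocol's Phase 2 data analysis plans only descriptive statistics at baseline, so the significance test is an addition in the SAP.

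**Between arms.** Under clinical outcomes, SAP section 5 says "Independent t-tests (or the non-parametric equivalent Mann-Whitney U) will be conducted to compare the scores of the experimental group and control group"; the protocol has the same plan. SAP section 6.3 lists the KDQOL-SF36, EQ-5D-5L and HADS at weeks 3, 6 and 12. SAP Table 1 shows all three also collected at baseline. The only other model is an analysis of variance for sub-groups.

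**Within arm.** A paired test (or Wilcoxon) will "compare the mean scores of the experimental before and after receiving the intervention". None is planned for the control arm.

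**Safeguards.** The SAP says that "no conclusions on the effectiveness of the intervention will be made from the results". The protocol's Phase 4 data analysis adds: "Costs and outcome measure data for both the intervention and control group will be presented using means and 95% confidence intervals".

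**The concern.** There are three linked problems.

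1. Chi-squared compares category frequencies. It suits gender, education and ethnicity in type. It does not fit age, vintage or a co-morbidity count, and it is sparse for a 9-point frailty scale at about 15 per arm. Nothing later in the plan depends on the answer.
2. The scores to be compared are not defined as follow-up values or changes from baseline, and no visit is named for the test. Two analysts could report different arm differences from the same data. Whichever form is meant, the baseline measurement is not used for adjustment, so the interval will usually be wider than it need be.
3. A before/after test in one arm cannot separate the intervention from drift or regression to the mean. A small p-value there could be read as a signal. The protocol's own sample-size discussion warns that significant results from feasibility studies tend to be reported opportunistically.

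**Working it through.** **Inputs.** The total sample is 30 (SAP section 4.1) and allocation is 1:1 (protocol, Randomisation), so 15 per arm. The documents give no SD, correlation or drift. I assume SD = 1 at both times, baseline/follow-up correlation r = 0.3, 0.5 or 0.7, independent patients, no loss to follow-up, and two-sided 0.05. The plan has no figure of its own to reproduce, because 30 was chosen by rule of thumb.

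**Chi-squared on a continuous variable.** Take 30 distinct values, 15 per arm. The table has 60 cells, each with expected count 0.5 and observed count 0 or 1. Each cell contributes 0.5²/0.5 = 0.5, so the statistic is 60 × 0.5 = 30.0 on 29 df, p = 0.414. This holds for any arrangement. With the arms completely separated a t-test gives p = 6 × 10⁻¹⁰; with them interleaved it gives p = 0.76. Chi-squared gives 0.414 both times, so it carries no information.

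**Chi-squared on frailty.** The mean expected count per cell with k occupied levels is 30/(2k): 3.75 for k = 4 and 1.67 for k = 9. How many levels will be occupied is unknown.

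**Precision of the arm difference.** The SE for follow-up scores is √(2/15) = 0.3651.

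- Follow-up score: t(0.975, 28) × 0.3651 = 0.748
- Change score: 0.748 × √(2(1−r))
- ANCOVA: t(0.975, 27) × 0.3651 × √((1−r²) × 27/26), where 27/26 allows for estimating the slope

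| 95% CI half-width (SD) | r = 0.3 | r = 0.5 | r = 0.7 |
|---|---|---|---|
| Follow-up score | 0.75 | 0.75 | 0.75 |
| Change score | 0.89 | 0.75 | 0.58 |
| ANCOVA | 0.73 | 0.66 | 0.55 |

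A simulation of 4000 trials gave root-mean-square ANCOVA half-widths of 0.729, 0.660 and 0.545.

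The variance of ANCOVA relative to follow-up scores is (1−r²) × 27/26 = 0.945, 0.779 and 0.530, a saving of 5.5%, 22% and 47%. Relative to change scores it is ((1+r)/2) × 27/26 = 0.675, 0.779 and 0.883, a saving of 32.5%, 22% and 12%.

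**Effect on the estimate.** A chance baseline difference of up to 1.96 × 0.3651 = 0.72 SD lies within the 95% range. A baseline imbalance of 0.5 SD is expected to shift the follow-up difference by 0.5r (0.25 SD at r = 0.5, 0.35 SD at r = 0.7) and the change difference by 0.5(r−1) (−0.25 and −0.15 SD). The two readings then differ by 0.5 SD, which is the imbalance itself.

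**One-arm paired test.** Suppose both arms drift by d with no intervention effect. With n = 15 and df = 14, the noncentrality is d√15/√(2(1−r)).

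| Chance of p<0.05 | r = 0.3 | r = 0.5 | r = 0.7 |
|---|---|---|---|
| d = 0.3 SD | 15% | 19% | 29% |
| d = 0.5 SD | 33% | 44% | 64% |

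**The case against.** The strongest reply is that none of this bears on what the trial is for. The clinical comparisons are exploratory, effectiveness conclusions are ruled out, and progression rests on recruitment and acceptability. That stands, and it limits how serious the point is.

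Other replies have partial force:

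- *Chi-squared was meant for the categorical items only.* SAP section 5 does separate categorical from continuous data for description. But the sentence on testing sets no such limit, and the protocol's list of baseline data includes the continuous items.
- *The natural reading is follow-up scores at the three listed weeks.* This is plausible, since change scores are never mentioned. Even so, ANCOVA is narrower than the follow-up comparison at every r shown, though at r = 0.3 the gain is only from 0.75 to 0.73 SD.
- *An unadjusted comparison of randomised arms is not an error.* Agreed; it is a less efficient choice when the baseline score is already in hand.
- *Control-arm means with intervals are already planned.* They are, so control-arm scores will be visible. But the interval for a change cannot be recovered from separate means at each visit, because it depends on the within-patient correlation.
- *The size rests on assumptions.* The correlation and drift are assumed. Allocation by dialysis days also conflicts with treating patients as independent, and would widen every interval above.

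**Conclusion.** The concern holds as an improvement the plan should make, and it does not threaten the primary outcome or the progression decision. The named baseline test does not fit age, vintage or co-morbidity count and has no later use. The arm comparison leaves the form of the score and the visit open and does not use the baseline value. The one-arm test can produce p<0.05 from drift alone.

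Over the assumed correlations of 0.3 to 0.7, adjustment brings the half-width to 0.73–0.55 SD, against 0.75 SD for follow-up scores or 0.89–0.58 SD for change scores. The one-arm test would reach p<0.05 in about 15–29% of trials under a 0.3 SD drift and 33–64% under 0.5 SD. All these figures assume 15 independent patients per arm, equal SDs and no loss to follow-up. They are illustrative, and the interval widths are optimistic given allocation by dialysis days.

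**What to change.** 1. **SAP section 5, secondary quantitative outcomes:** delete the baseline chi-squared tests. Describe the arms at baseline as sections 5 and 6.2 already plan.
2. **SAP section 5, clinical outcomes, and the protocol's Phase 2 data analysis:** define the outcome as the follow-up score at weeks 3, 6 and 12, and name the total, subscale or index used for each instrument. Report the baseline-adjusted mean difference (ANCOVA) with its 95% CI at each week. Keep a rank-based check, such as the planned Mann-Whitney, or a bootstrap interval for skewed scores. State that adjustment does not remove confounding or clustering by dialysis days.
3. **Same two places:** report change from baseline with its 95% CI in both arms. If the experimental-arm paired test is kept for comparison with the pre/post literature, print the control arm's change beside it.

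The cost is wording: item 1 in the SAP alone, items 2 and 3 in both documents. No new data are needed, since every score is already in SAP Table 1.
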